14.5.2 Primary Safety

The primary safety endpoint will be tested with the following non-inferiority hypothesis test:

 H_0 : St - Sc \geq 0.058 H_A : St - Sc < 0.058

where St and Sc are the proportion of subjects with primary safety endpoints in the treatment and control groups respectively at 12 months (study day 365) and 0.058 represents the non-inferiority margin. The hypothesis will be evaluated using a one-sided 97.5% confidence interval for the difference in event rates based on the Kaplan-Meier estimate. If the one-sided upper confidence bound for the difference is less than the non-inferiority margin, the objective will be met, and the treatment group will be non-inferior to the control group for the primary safety endpoint.

14.5.3 Secondary Endpoints

The secondary endpoints defined in Section 8.3.3 will be summarized with descriptive statistics. Hypothesis tests for secondary endpoints are planned to use a gatekeeping approach for specific performance endpoints listed below. All other secondary endpoints will be summarized with descriptive statistics for completeness.

14.6 Additional Analyses

The following data will be summarized using descriptive statistics presented by treatment group in the ITT Randomized, Attempted, and Implanted populations, as applicable:

- Subject enrollment and data compliance by site and visit (data compliance at each visit is
 the percentage of subjects whose data forms have been collected and entered divided by
 the percentage of subjects whose forms should have been collected and entered).
- Frequency (number and percentage of subjects) with each type of concomitant medication.
- Frequency (number and percentage of subjects) with each site-reported Treatment Emergent AE overall and by MedDRA system organ class and preferred term (a treatment emergent AE is an AE that started or worsened during or after the index procedure).
- Frequency (number and percent of subjects) with each site-reported Treatment Emergent Serious AE overall and by MedDRA system organ class and preferred term.
- Frequency (number and percent of subjects) with each site-reported Treatment Emergent
 AE or SAE, by CEC-adjudicated relationship to the investigational device or procedure
 and CEC-adjudicated sub-classification as implant-related or delivery system-related.
- Protocol deviations (number and percentage of subjects with each deviation type).

Detailed listings on primary and secondary endpoints, site-reported AEs, and protocol deviations will be provided, as necessary.

14.7 Poolability and Subgroup Analyses

All investigational sites will follow the requirements of a common protocol and standardized data collection procedures and forms. Poolability of the primary effectiveness and primary safety endpoints across investigational sites will be evaluated using Cox regression models with fixed effects for treatment, site, and treatment by site interaction. If a p-value for the interaction effect is <0.15, additional exploratory analyses will be performed to understand any variations in outcome by site.

Similar analysis will be performed for geography (US vs. outside of the US) as well as subject subgroups defined by the following baseline characteristics: age, sex, race, ethnicity, CHA2DS2-VASc, HAS-BLED, device type (i.e., Initial CLAAS System, Next Generation CLAAS System, Watchman, Amulet), implant size, and AF pattern, examining the potential interaction of subgroup and treatment group.

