	Appendix E provides a summary of the Sub-Study with statistical rationale.
Medicare Considerations	The study eligibility criteria include subjects that are largely identified in the Medicare population. As such, the randomized trial design is considered adequate to characterize the safety and effectiveness of the CLAAS System and will appropriately support the CMS criterion for coverage.
Sample Size	The sample size requirements for each of the study cohorts is listed below.
	Roll-in Phase: a maximum of 300 subjects can be enrolled as roll-in cases.
	RCT Phase: Up to one thousand six hundred (1600) subjects will be enrolled in the randomized control trial.
Randomization	Randomization will be 1:1 to CLAAS Device (Investigational) versus currently marketed LAAO device (Control) using block randomization that is stratified by site.
Investigational Sites	Up to one hundred (100) investigational sites in North America, five (5) sites in Japan, and up to fifteen (15) sites in EU/EEA and Central Asia will be included in this study. The United States will account for ≥ 50% of the total subjects enrolled in the RCT cohort. Further, no more than 15% of the maximum sample size for the randomized trial will be enrolled by a single site.
	An ongoing list of all investigational sites shall be maintained in Sponsor files
Study Duration/ Follow-up Period	The trial is expected to take approximately 3 years to enroll, and each subject will be followed for a total of 5 years.

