8.3 Number of Required Subjects

The sample size requirements for each of the study cohorts:

8.3.1 Roll-in Phase: Up to 300 subjects study-wide may be implanted with the CLAAS Implant as roll-in cases, Investigational sites that implanted 3 subjects with the Initial CLAAS system will be permitted to implant one additional subject with the Next Generation CLAAS System.

Additional investigational sites will be permitted to implant up to a maximum of 3 roll-in subjects (Initial CLAAS System and Next Generation CLAAS System combined). The number of cases is determined through the training and proctoring process and is based upon demonstrated proficiency.

- **8.3.2 RCT Phase**: Up to one thousand six hundred (1600) subjects will be enrolled in the randomized control trial. The sample size is based on the power requirements for the primary effectiveness endpoint and was determined via simulation. With a non-inferiority margin of 3.2%, and one-sided alpha level of 0.025, the sample size of 1600 subjects should provide approximately 85% power for the hypothesis test of non-inferiority accounting for a 10% attrition rate. This sample size is also expected to provide greater than 80% power for the hypothesis test for the primary safety endpoint with a margin of 5.8% and a one-sided 0.025 alpha level. It should be noted that >50%_of the subjects enrolled in the RCT phase will be from the US and no more than 15% of the data will be from one site.
- **8.3.3 Conscious Sedation Single Arm Sub-study:** The sub-study is designed to demonstrate non-inferiority in CLAAS Implant success compared to the CLAAS arm of the RCT based on the 45 Day Endpoint. It is estimated that a total sample size of 130 subjects (including 6% attrition) is required to demonstrate non-inferiority. This estimated sample size will be verified and adjusted,

if necessary, based on the observed rate of CLAAS Implant success rate in the RCT, prior to initiation of the sub-study. Appendix E provides a summary of the Sub-Study with statistical rationale. This Sub-Study will be identified with a separate NCT number from the randomized controlled trial (NCT06049615).

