14.1 Sample Size Rationale

14.1.1 Effectiveness Endpoint

The sample size is driven by the power requirements for the primary effectiveness endpoint and was determined via simulation.

The 18-month study endpoint is defined as the composite of ischemic stroke or systemic embolism through 18 months. The estimated event rate used for power calculations is 4.14%. The estimated rate has been derived from the reported rate for WATCHMAN FLX through 12 months and Amulet through 18 months as described below.

The 12-month CEC-adjudicated major clinical event rates of 2.6% and 0.3% were reported for ischemic stroke and systemic embolism respectively (21) for WATCHMAN-FLX, which is the most prevalent product in use). The values of 2.6% and 0.3% were summed to produce a 12-month estimated rate of 2.9%. A linearized rate over the time from between 12 and 18 months was calculated to arrive at the final estimated anticipated rate of 4.4%. This reflects a 50% increase in the event rate from 12 to 18 months. For Amulet, the reported rate of ischemic stroke and systemic embolism was reported as 2.8% at 18 months. (26)

It is anticipated that the enrollment of control cases in CONFORM, will comprise approximately 80% WATCMAN-FLX cases and approximately 20% of Amulet cases. Using a weighted average of event rates based on this composition yields an overall estimated rate of 4.1%.

With a non-inferiority margin of 3.2%, and one-sided alpha level of 0.025 the sample size of up to 1600 subjects should provide greater than 85% power for the hypothesis test of non-inferiority accounting for a 10% attrition rate.

A non-inferiority margin of 3.2% is reasonable given precedent of similarly sized margins in previous studies, the expected underlying event rates, and power requirements for the study. For an expected event rate of 4.1%, a 3.2% margin corresponds to a relative increase of 78%.

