14.1.2 Safety Endpoint

The planned sample size is expected to provide sufficient power for the hypothesis test for the primary safety endpoint. Specifically, assuming an underlying safety event rate in both groups of 15% (similar to those reported for the Amulet study (26) with a 5.8% non-inferiority margin, a total of approximately 1200 subjects would provide greater than 80% power based on an un-pooled ztest at the one-sided 0.025 alpha level. Given the larger sample size required for the primary effectiveness endpoint, this approximation should be reasonable, and the planned sample size provide a high degree of power. A margin of 5.8% is approximately 38% of the value of the expected rate, reflecting a clinically reasonable non-inferiority margin given the underlying expected event rate.

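### The fixed-effect site-poolability test in Section 14.7 cannot inform on the primary effectiveness endpoint, with about 0.5 events per site at the 120-site ceiling

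*Protocol*

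**What the plan says.** Section 14.7 fixes the model for both primary endpoints: "Cox regression models with fixed effects for treatment, site, and treatment by site interaction". It then fixes the trigger: "If a p-value for the interaction effect is <0.15, additional exploratory analyses will be performed". A similar analysis follows for US versus outside-US and for baseline subgroups. The section does not say whether the interaction is judged by a Wald, likelihood-ratio or score test. The opening of Section 14 sends further poolability detail to the SAP, which was not available for this review.

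The figures that determine whether the model can work are elsewhere in the protocol:

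- Synopsis, the row on sites, reads: "Up to one hundred (100) investigational sites in North America, five (5) sites in Japan, and up to fifteen (15) sites in EU/EEA" (the last group also takes in Central Asia). There is a cap, "no more than 15% of the maximum sample size for the randomized trial will be enrolled by a single site", but no minimum per site.
- Section 8.3: "Up to one thousand six hundred (1600) subjects will be enrolled in the randomized control trial".
- Section 14.1.1: "The estimated event rate used for power calculations is 4.14"% (ischemic stroke or systemic embolism through 18 months).
- Section 14.1.2: "assuming an underlying safety event rate in both groups of 15"% (12-month safety composite).

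**The concern.** A fixed treatment-by-site interaction asks each site for its own hazard ratio. A site with no event contributes nothing. A site with events in only one arm has an estimate that runs to plus or minus infinity. When most sites fall into those two classes, the Wald statistic collapses because the standard errors explode. The chi-square reference for the likelihood-ratio statistic also fails, and its degrees of freedom become a matter of software convention.

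At stake is how the result will be read. A non-significant interaction for effectiveness could be taken as evidence that sites agree when the test had no ability to say otherwise. A significant one could start exploratory work on an artefact.

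**Working it through.** **Stated power, reproduced first.** Section 14.1.1: "With a non-inferiority margin of 3.2%, and one-sided alpha level of 0.025". Section 8.3 gives about 85% power with 10% attrition. With 1600 × 0.90 / 2 = 720 per arm and an unpooled z-test:

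- SE = √(2 × 0.0414 × 0.9586 / 720) = 0.0105
- power = Φ(0.032 / 0.0105 − 1.96) = Φ(1.09) = 86.2%

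A Kaplan-Meier simulation with 10% attrition (4000 runs) gives 88.0%. The protocol's figure is reproduced, so 4.14% is a fair basis for counting events.

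**Events and parameters.**

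- Sites: 100 + 5 + 15 = 120. Parameters: 1 treatment + 119 site + 119 interaction = 239.
- Effectiveness: 1600 × 0.0414 = 66 events; 1440 × 0.0414 = 60 if dropouts contribute nothing; about 63 with gradual attrition.
- Safety: 1600 × 0.15 = 240 events; 1440 × 0.15 = 216.
- Effectiveness events per site: 66.2 / 120 = 0.55; per site-arm 0.276.
- With equal sites and Poisson counts, P(no event) = e^(−0.552) = 0.58 per site and e^(−0.276) = 0.76 per site-arm.
- Expected sites with any event: 120 × 0.42 ≈ 51. Expected sites with events in both arms: 120 × 0.24² ≈ 7.

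**Operating characteristics.** Cox models with the stated fixed effects were fitted to simulated trials: 1600 subjects, 1:1 within 120 sites, 10% attrition, site sizes equal or skewed (gamma, coefficient of variation 1). There were 200 runs per effectiveness scenario and 150 per safety scenario. Real heterogeneity means a between-site SD of 1.0 in the log hazard ratio. Site sizes and this SD are assumptions, since the protocol gives neither. A calibrated test fires 15% of the time with no heterogeneity. Ranges span equal and skewed sites.

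| Fires at p<0.15 | Effectiveness, none | Effectiveness, SD 1.0 | Safety, none | Safety, SD 1.0 |
|---|---|---|---|---|
| Wald | 0% | 0% | 0% | 0% |
| Likelihood ratio, 119 df | 0% | 0% | 19–69% | 99% |
| Likelihood ratio, df = sites with events | 95–99.5% | 100% | 97–99% | 100% |
| Score, 119 df | 0–0.5% | 0–1.5% | 5–19% | 87–91% |
| Score, df = sites with events | 16–32% | 45–74% | 40–75% | 99–100% |

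With no heterogeneity, about 44 to 49 sites had any effectiveness event and about 7 to 8 had one in both arms, in line with the Poisson count. A zero in 200 runs is compatible with a true rate up to about 3/200 = 1.5%.

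A separate conditional-binomial approximation for effectiveness, with no heterogeneity, gave 0% for the likelihood-ratio test on 119 df and 83–95% on reduced df. For safety on 119 df it gave 0.5–25% with no heterogeneity and 85–99.6% at SD 1.0. The safety null rate thus depends strongly on site layout and method, but the response to heterogeneity does not disappear.

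**Fewer sites than the ceiling.** Skewed sites, no heterogeneity, effectiveness, 40 runs each: the Wald test fires 0% at both 80 and 50 sites. The reduced-df likelihood-ratio test fires 82.5% and 67.5%.

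**Combining sites into equal groups.** No heterogeneity, 400 runs, target 15% (simulation SE about 1.8 points):

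| Groups | Effectiveness: Wald / LR / score | Safety: Wald / LR / score |
|---|---|---|
| 4 | 12 / 17 / 15% | 16 / 16 / 16% |
| 8 | 1 / 24 / 16% | 14 / 16 / 15% |
| 12 | 0 / 28 / 15% | 11 / 17 / 15% |
| 20 | 0 / 40 / 12–16% | 6 / 20 / 16% |

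For effectiveness, Wald and likelihood-ratio tests are near nominal only at about 4 groups. The score test tolerates more.

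**The case against.** **The SAP may already deal with this.** Section 14 names poolability among the topics detailed there. Small-site rules, minimum site size and the choice of test are ordinary SAP content, so their absence from the protocol is not a fault. That stands. But Section 14.7 itself commits to fixed site and interaction effects and to the 0.15 threshold, and it is this stated rule that does not work. A random-effects SAP would contradict it; an SAP that combines small sites would repair it.

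**Nothing decisive hangs on the test.** This also stands. A reader might infer that permission to pool, or study success, depends on it. The protocol does not say so: the trigger leads only to exploratory analyses, the primary tests in Sections 14.5.1 and 14.5.2 are Kaplan-Meier differences against fixed margins, and Section 8.5 defines success by those two endpoints alone.

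**Safety is different.** A reader might extend the never-or-always behaviour to both endpoints. With about 216 to 240 safety events that is not supported. The Wald test still never fires and the likelihood-ratio test over-fires in most layouts, but likelihood-ratio and score versions fire far more often when sites truly differ.

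**One variant escapes, and 120 is a maximum.** For effectiveness, a score test with df cut to sites with events is neither never nor always. The protocol does not name it, and its null rate still reaches 32% with skewed sites. Fewer sites reduce the problem without removing it at 50.

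**Conclusion.** The point holds for the primary effectiveness endpoint. With about 60 to 66 events over up to 120 sites, the Wald test and the 119-df likelihood-ratio test fire about 0% of the time whether or not sites differ. The reduced-df likelihood-ratio test fires about 83% to 99% of the time when they do not. A result in either direction would say almost nothing about site heterogeneity in effectiveness.

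For safety the supported statement is narrower: calibration is poor to a degree set by the test and the site sizes, but the check is not blind.

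The harm is an uninformative poolability check, not a threat to the primary analyses. The sparsity follows from the protocol's own figures. The exact firing rates rest on assumed site-size distributions, an assumed heterogeneity SD of 1.0, and 120 active sites.

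**What to change.** In Section 14.7, and in the SAP if it does not already do so, replace the fixed treatment-by-site test for effectiveness with one of the following:

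- **(a)** A Cox model with random site and random treatment-by-site effects, reporting the interaction variance with its interval. Check the test's calibration by simulation or permutation; that calibration was not examined here.
- **(b)** Sites combined within region, by a rule fixed without outcome data, into about 4 groups, or up to about 8 with a score test. Name the score test as the basis of the p<0.15 rule.

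More groups can be used for safety: at 8 groups all three tests are near 15%, and the score test remains so at 20. Keep the US versus outside-US comparison as stated.

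The cost is wording only, with no added data or patients. The downside is that individual small-site effects are no longer tested, which about 0.5 events per site could not support anyway. Power to detect heterogeneity in effectiveness will stay low under either option, and the text should say so, so that a non-significant result is not read as proof of homogeneity.

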14.8 Missing Data Handling

All attempts will be made to limit the amount of missing data. The number of evaluable observations will be reported in analysis so that extent of missing data can be assessed. In addition, survival methods will be used to capture the extent of follow-up data available for subjects who are lost or withdrawn from the study.

Tipping point sensitivity analyses will be performed to assess the impact of missing endpoint status for each of the primary effectiveness and primary safety endpoints. These will be based on a Cox regression model with the imputed endpoint rate for censored subjects varied to determine results that would change the study conclusions. This will incorporate multiple imputation, based on randomly imputing events for censored subjects from the on randomized group specific Kaplan-Meier estimated survival distribution after the censoring time.

14.9 Administrative Analyses

An Administrative Analysis of the 1-year safety data and TEE assessments are planned. Access to this information will be restricted under Confidentially Agreements to prevent disclosure of data from introducing bias. The Administrative Analysis will be performed by an independent unblinded statistician separate from the personnel involved with anything related to study operations. There are no planned sample size or study modifications for the administrative analysis.

14.10 Measures to Minimize Bias

Randomization assignment provides protection against confounders, both measured and unmeasured. Pre-specified endpoints and analysis plans also minimize bias. To decrease the variability of clinical outcome measurements, all site-reported cardiovascular adverse events and all potential endpoint events will be adjudicated by an independent CEC according to standardized endpoint definitions, and the relationship of these events to the study device will also be adjudicated and sub-classified as implant-related or delivery system-related. The CEC will be blinded to the treatment assignment to the extent possible to further minimize bias. In addition, independent imaging core laboratory analysis will provide objective determination of peri-device residual leak, and the presence of thrombus.

15 Publication Policy

Conformal and the Principal Investigator(s) are committed to the publication and widespread dissemination of the results of the study in the scientific community. This study represents a joint effort between the Sponsor and the Principal Investigator(s); as such, the parties agree that the recommendation of any party concerning manuscript or text shall be taken into consideration in the preparation of final scientific documents for publication or presentation. Conformal will submit trial results for publication (regardless of trial outcome) following the conclusion or termination of the trial.

A Publication Agreement will be signed between the principal investigator and the sponsor either as a separate Publication Agreement or within the Clinical Trial Agreement.

The investigator or site may not publish any information that the sponsor believes to be confidential information. The publication of the initial results of the CONFORM Pivotal Trial shall be subject to the review and release of sponsor's publication committee, which shall confer with the site regarding such publication.

Publication guidelines will be followed according to the International Committee of Medical Journal Editors (ICMJE). Within 21 days of enrollment of the first subject into the CONFORM Pivotal Trial, this clinical trial will be registered on ClinicalTrials.gov. A full report of the pre-specified outcomes, regardless of trial results, will be made public through the ClinicalTrials.gov website according to the requirements of Section 801 of the FDA Amendments Act. If this clinical trial is terminated early, Conformal will make every effort to hasten the release of the pre-specified outcomes through the ClinicalTrials.gov website.

16 Data Collection and Monitoring

16.1 Data Collection and Monitoring

All required data for this study will be collected on standardized Case Report Forms (CRFs) using an electronic data capture system (EDC). The verification, validations and security of the EDC may be noted in the Data Management Plan and/or related documents. The EDC system

will meet applicable requirements as set forth by FDA or other regulatory authorities. An audit trail will be available for tracking all data that the EDC use enters, modifies or deletes.

The data entered into the EDC will be fully validated as described in the Data Management Plan and/or related documents, which may include using clinical investigation-specific range and consistency checks and database listings. Queries may be issued to the site via the EDC system and resolved by the investigator or his/her designee using the EDC. Data validation will be completed on a regular basis. The entire database will be re-validated to ensure that there are no outstanding data discrepancies prior to database lock. Any changes to the database after that time will require written agreement by the Sponsor.

The investigator (or designated hospital staff) will ensure primary data collection based on source-documented hospital chart reviews.

Monitoring will be performed by the Sponsor and/or its designee(s) to ensure that the investigator and his/her study team conduct the clinical investigation in accordance with contract specifications, this protocol, the Declaration of Helsinki, ICH-GCP, ISO 14155:2020, 21 CFR Part 812, and other applicable FDA (and other regulatory authorities, as applicable) and local regulations, and to ensure adequate protection of the rights and safety of subjects and the quality and integrity of the resulting data. All monitors will receive study-specific training on the Clinical Investigation Plan, the eCRF, and the use of the investigational device in accordance with Sponsor SOPs.

Submitted trial data will be verified against subject charts and other sources containing original records of subject data. Source document verification will occur in accordance with the prespecified study-specific Monitoring Plan. All study endpoints will be 100% source data verified. The Investigator/institution will permit direct access to source data/documents for trial-related monitoring, audits, IRB/REB/EC review and regulatory inspections to be performed. The frequency of monitoring will be based upon enrollment, study duration and compliance,

Progress of the trial will be monitored by:

- On-site or remote review, as deemed appropriate by the Sponsor
- Telephone communications between site personnel (e.g., Site Investigator, Trial Coordinator) and trial monitors, as appropriate
- Review of CRFs and associated clinical records
- Review of regulatory documents

If a monitor becomes aware of a significant non-compliance with the requirements mentioned above, the Sponsor will be notified by the monitor. The Sponsor will evaluate the non-compliance and may assess if a corrective and preventative action plan is applicable to secure compliance. Immediate actions may be taken to secure compliance and should be documented. If necessary, the Sponsor may halt shipments of the investigational device to the Investigator and terminate the Investigator's participation and enrollment in the investigation. The Investigator will be required to return all unused devices to the Sponsor.

After each monitoring visit, the Monitor will send to the Investigator a letter summarizing the monitoring visit. A monitoring report will be provided to the Sponsor. The report will include the date of the monitoring visit, the site name, the name of the monitor, the name of the Investigator, the names of other individuals present for the monitoring visit, items reviewed during the visit, findings, and any required follow-up action items. The Investigator will be responsible for ensuring

that follow-up actions needed to resolve issues at the site are completed in an accurate and timely manner.

Final monitoring visits at the investigational sites will be conducted at the close of the study at the site. The purpose of the final visit is to collect any outstanding study documents, ensure that the Investigator's files are accurate and complete, review record retention requirements with the Investigator, make a final accounting of all study supplies, provide for appropriate disposition of any remaining supplies, and ensure that all applicable requirements are met for the study.

